10.1.6.2. Data Recording and Documentation

Data collection will involve the use of the sponsor's EDC system, to which only authorized personnel will have access. Participant's data are to be entered into the EDC system by the investigator or designee using their assigned EDC user account. After data entry into the EDC system by the investigator or designee, a combination of manual and programmatic edit checks will be used to review the data for completeness, logic, and adherence to study protocol. As a result of these edits checks, data monitoring and reviews, queries may be electronically issued to the site and should be answered electronically via the EDC system.

Each query will carry identifying information (assigned username, date, and time) to assist the sponsor and the investigator on the origin of the data clarification request and the response provided by the investigator. All data changes made to the participant's data via a data query will be approved by the investigator prior to final database lock.

After all data have been reviewed and all issues have been resolved, the database will be locked.

All data collected in the context of this study will be stored and evaluated per regulatory requirements and applicable guidance for electronic records. Also, data will be stored and evaluated in such a way as to guarantee participant confidentiality in accordance with the legal stipulations applying to confidentiality of data. Study records (eg, copies of eCRFs, laboratory reports, participant diaries, regulatory documents) will be retained at the site, along with adequate source documentation, according to FDA and ICH requirements. All study records must be available for inspection by the sponsor, its authorized representatives, and health authorities.

10.1.6.3. Data and Safety Monitoring Board

An independent DSMB will review interim safety data at defined intervals throughout the study or ad hoc if needed. The DSMB will communicate their recommendations to the sponsor after each meeting but will serve in an advisory capacity only. Further details of the DSMB (composition, policy, and procedures) are specified in a separate DSMB Charter.

10.1.7. Source Documents

- Source documents provide evidence for the existence of the participant and substantiate the integrity of the data collected. Source documents are filed at the investigator's site.
- Data reported on the CRF or entered in the eCRF that are transcribed from source documents must be consistent with the source documents or the discrepancies must be explained. The investigator may need to request previous medical records or transfer records, depending on the study. Also, current source documents must be available.

10.1.8. Study and Site Closure

The sponsor designee reserves the right to close the study site or terminate the study at any time for any reason at the sole discretion of the sponsor. Study sites will be closed upon study completion. A study site is considered closed when all required documents and study supplies have been collected and a study-site closure visit has been performed.

The investigator may initiate study-site closure at any time, provided there is reasonable cause and sufficient notice is given in advance of the intended termination.

Reasons for the early closure of a study site by the sponsor or investigator may include but are not limited to:

- Failure of the investigator to comply with the protocol, the requirements of the IRB/IEC or local health authorities, the sponsor's procedures, or GCP guidelines
- Inadequate recruitment of participants by the investigator
- Discontinuation of further study intervention development

10.1.9. Publication Policy

- Allergan as the sponsor has proprietary interest in this study. Authorship and manuscript composition will reflect joint cooperation between multiple investigators and sites and Allergan personnel. Authorship will be established prior to the writing of the manuscript. As this study involves multiple centers, no individual publications will be allowed prior to completion of the final report of the multicenter study except as agreed with Allergan.
- The sponsor will comply with the requirements for publication of study results. In accordance with standard editorial and ethical practice, the sponsor will generally support publication of multicenter studies only in their entirety and not as individual site data.
- Authorship will be determined by mutual agreement and in line with International Committee of Medical Journal Editors authorship requirements.

10.1.10. Compliance with Protocol

The investigator is responsible for compliance with the protocol at the investigational site. A representative of the sponsor will make frequent contact with the investigator and his/her research staff and will conduct regular monitoring visits at the site to review participant and study intervention accountability records for compliance with the protocol. Protocol deviations will be discussed with the investigator upon identification. The use of the data collected for the participant will be discussed to determine if the data are to be included in the analysis. The investigator will enter data that may be excluded from analysis as defined by the protocol deviation specifications. Significant protocol deviations will be reported to the IRB/IEC according to the IRB/IEC's reporting requirements.

Deviating from the protocol is permitted only if absolutely necessary for the safety or clinical management of the participants and must immediately be reported to the sponsor. Protocol deviations should be reported to the sponsor (either verbally or electronically) in a timely manner from the day of discovery.

Protocol deviations that may impact participant's rights (eg, failure to obtain informed consent prior to initiating study procedures), safety, or well-being (eg, deviations that resulted in an SAE, exposure during pregnancy), or the integrity and authenticity of the study data should be reported to the sponsor within 24 hours, if possible.

The IRB/IEC must be notified according to the criteria and time period dictated by the IRB/IEC associated with this study.

10.1.11. Study Documentation

The investigator must provide the following to the sponsor before the start of the study:

- For sites in the United States, a completed and signed Form FDA 1572. If, during the course of the study, any changes are made that are not reflected on Form FDA 1572, a new Form FDA 1572 must be completed and returned to the sponsor for submission to the FDA
- A fully executed contract
- For sites in the United States, the curricula vitae for the investigator and all subinvestigators listed on Form FDA 1572, including a copy of each physician's license
- A copy of the original IRB/EC approval for conducting the study. If the study is ongoing, renewals must be submitted at yearly intervals. All subsequent modifications must be submitted and approved by the IRB/EC, as stated in Section 10.1.1.
- A copy of the IRB/EC-approved parent/LAR, Caregiver ICFs, and participant's assent
- A copy of the HIPAA authorization form, or other local privacy applicable forms
- A list of the IRB/EC members or the US Department of Health and Human Services general assurance number
- The Investigator's Statement page in this protocol signed and dated by the investigator
- For sites in the United States, financial disclosure agreement completed and signed by the investigator and all subinvestigators listed on Form FDA 1572. The investigator and all subinvestigators will provide an updated financial disclosure agreement to the sponsor 1 year after the completion of the study
- For sites in the EU and European Economic Area the study must be conducted in accordance with the national legislation that is set forth in the Directives 2001/20/EC, 2001/83/EC, and 2005/28/EC (and the Regulation [EU] No 536/2014 when in force).

10.2. Appendix 2: Clinical Laboratory Tests

Blood and urine samples for clinical laboratory tests will be collected as detailed in the SoAs (Section 1.4 and Section 1.5). During the screening period, the investigator will assess the clinical significance of any values that are outside the reference ranges provided by the central laboratory. Participants with abnormalities judged to be clinically significant will be excluded from the study.

Participants with clinically significant electrolyte abnormalities that are considered to be secondary to diarrhea (ie, an AE of special interest) must be reported to the sponsor within 24 hours on an SAE form if considered to be serious. Nonserious events do not require submission on an SAE form; rather, these events only need to be entered into the eCRF (Appendix 3). If the AE is assessed as causally related to the use of study intervention, the participant should be discontinued from the study; however, the sponsor and investigator may discuss individual participants and AEs to make this decision.

Clinical laboratory levels that will be measured are summarized in [Table 10-1](#).

The clinical significance of a positive urine drug screen will be assessed by the investigator. Participants will be excluded from study participation if urine drug screening results are positive for cocaine, barbiturates, opiates, or cannabinoids.

For female participants of childbearing potential urine pregnancy test will be obtained at Screening (Visit 1) for participants who enroll \leq 28 days from last study intervention and serum pregnancy test will be obtained at Screening (Visit 1) for participants who enroll $>$ 28 days from last study intervention. Urine pregnancy test will be performed for all participants at the Day 1 Visit (Visit 2) prior to dosing as specified in the SoAs (Section 1.4 and Section 1.5) and Visits 4 to 7 during study intervention for FC participants and Visits 4 to 10 for IBS-C participants. Positive results on the pregnancy test at Screening (Visit 1) or Day 1 Visit (Visit 2) will exclude participants from participating in the study. Positive pregnancy test results during the study will result in participant termination from the study. Investigators must inquire at every study visit about the use of acceptable methods of contraception in participants of childbearing potential who are, or become, sexually active. Repeat pregnancy tests may be performed at the investigator's discretion at other times during the study.

Other laboratory assessments may be repeated at any visit if there was an abnormal finding at the most recent previous evaluation or if additional information is clinically necessary to

appropriately evaluate the participant's current condition, follow up, and/or manage an adverse experience.

A central laboratory will be used to evaluate all urine (except urine pregnancy tests) and blood samples, which will be collected, processed, and stored according to the instructions provided by the laboratory. The urine pregnancy tests will be completed on site at the study site.

- Protocol-specific requirements for inclusion or exclusion of participants are detailed in Section 5 of the protocol.
- Additional tests may be performed at any time during the study as determined necessary by the investigator or required by local regulations.

Table 10–1 Protocol-Required Safety Laboratory Assessments

Laboratory Assessments		Parameters		
Hematology	Platelet count Red blood cell (RBC) count Hemoglobin Hematocrit	RBC indices: MCV MCH MCHC	White blood cell (WBC) count with differential (absolute): Neutrophils Lymphocytes Monocytes Eosinophils Basophils	
Clinical Chemistry ^a	Blood urea nitrogen (BUN) Creatinine Glucose nonfasting	Potassium Sodium Bicarbonate Magnesium Phosphate Total Protein Total Bilirubin Calcium	Aspartate aminotransferase (AST) Alanine aminotransferase (ALT) Alkaline phosphatase	Total, direct and indirect bilirubin Total protein Total Cholesterol chloride, albumin
Routine Urinalysis	
 Specific gravity pH, glucose, protein, blood, ketones microscopic examination (if blood or protein is abnormal) 			
Other Screening Tests	
 Urine alcohol and drug screen (to include at minimum: benzoyllecgonine (cocaine), barbiturates, amphetamines, benzodiazepines, cannabinoids, ethanol, opiates) For female participants of childbearing potential: Serum human chorionic gonadotropin (hCG) pregnancy test at screening for LIN-MD-62, LIN-MD-63, and LIN-MD-64 completers who enroll > 28 days from last study intervention; urine pregnancy test for participants who enroll ≤ 28 days from last study intervention^b. LIN-MD-64 completers who enroll in this study on the same day as their EOT Visit in the lead-in study do not need to repeat the urine pregnancy test. For all female participants of childbearing potential: Urine pregnancy test at Visit 2 prior to dosing and at Visits 4 to 7 for FC participants and Visits 4 to 10 for IBS-C participants during study intervention^b. All study-required laboratory assessments will be performed by a central laboratory, with the exception of urine pregnancy test that will be performed locally at the site at all visits during study intervention. 			

^a Details of liver chemistry stopping criteria and required actions and follow-up assessments after liver stopping or monitoring events are provided in [Appendix 9](#).

^b Local urine testing will be standard for the protocol unless serum testing is required by local regulation or IRB/IEC.

Investigators must document their review of each laboratory safety report.

10.3. Appendix 3: Adverse Events: Definitions and Procedures for Recording, Evaluating, Follow-up, and Reporting

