The overall prevalence of IBS in the pediatric population is low. IBS prevalence in children across the United States, based on parental reports, ranges from 1.2% to 2.9%, while school-based studies in Colombia and Sri Lanka found a prevalence of IBS of 4.9% and 5.4%, respectively ([Hyams 2016](#)). In adults, although not life-threatening, because of its chronic relapsing course, IBS is associated with impaired quality of life and high direct and indirect medical costs such as absenteeism from work ([Thompson 1999](#)). In children and adolescents, IBS has been associated with significant impairment as increased rates of school absenteeism, health-care utilization and family disruption are common ([Chiou and Nurko 2010](#)).

The primary objective of LIN-MD-66 is to assess the long-term safety of linaclotide administered to participants with FC (total exposure with linaclotide for 24 weeks) or IBS-C (total exposure with linaclotide for 52 weeks) who have completed study intervention in Study LIN-MD-62, LIN-MD-63, or LIN-MD-64.

Objectives and Assessments:

Objectives	Assessments
Primary The objective of this study is to assess the long-term safety of linaclotide in pediatric participants with FC (total exposure with linaclotide for 24 weeks) or IBS-C (total exposure with linaclotide for 52 weeks) who have completed study intervention in Study LIN-MD-62, LIN-MD-63, or LIN-MD-64.	The safety assessments will include monitoring of adverse events (AEs), clinical laboratory assessments (clinical chemistry, complete blood count [CBC], urinalysis), vital sign measurements (including postural vital signs), electrocardiograms (ECGs), physical examinations, height, and weight.

Overall Study Design:

LIN-MD-66 is a long-term safety study with 24 weeks (FC participants) or 52 weeks (IBS-C participants) of linaclotide exposure that will enroll pediatric participants (6-17 years of age) with FC or IBS-C who completed study intervention in Phase 2 study LIN-MD-62 or LIN-MD-63, or Phase 3 study LIN-MD-64, based on the individual study criteria. For FC participants enrolling from studies LIN-MD-62 and LIN-MD-64, and IBS-C participants enrolling from study LIN-MD-63, linaclotide treatment will be open-label. For IBS-C

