9.4.2. Clinical Laboratory Assessments

Descriptive statistics for clinical laboratory values (in SI units) at baseline and changes from baseline at each assessment timepoint will be presented by study intervention group for each clinical laboratory assessment.

The criteria for PCS laboratory values will be detailed in the SAP. The number and percentage of participants who have PCS postbaseline clinical laboratory values will be tabulated by study intervention. The percentages will be calculated relative to the number of participants who have available non-PCS baseline values and at least 1 postbaseline assessment. The numerator will be the total number of participants with at least 1 PCS postbaseline value. A supportive listing of participants with PCS postbaseline values will be provided for the Safety Population.

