9.3 Analysis of Laboratory Data

Descriptive statistics for clinical laboratory values (in International System of Units [SI] units) and changes from the baseline values at each assessment time point will be presented by study intervention group for the following clinical laboratory parameters.

Hematology: Platelet count, red blood cell (RBC) count, hemoglobin, hematocrit, RBC indices (mean corpuscular volume, mean corpuscular hemoglobin, and mean corpuscular hemoglobin concentration), white blood cell count with differential (Neutrophil, Lymphocytes, Monocytes, Eosinophils, Basophils), and

Chemistry: Blood urea nitrogen, creatinine, glucose, potassium, sodium, bicarbonate, magnesium, phosphate, total protein, calcium, aspartate aminotransferase (AST), alanine aminotransferase (ALT), alkaline phosphatase, total bilirubin, direct and indirect bilirubin, total cholesterol, chloride, albumin, and

Urinalysis: Specific gravity and pH

Clinical laboratory test values will be considered potentially clinically significant (PCS) if they meet either the lower-limit or higher-limit PCS criteria listed in Table B-1 in [Appendix B](#). The number and percentage of participants who have at least one PCS post-baseline clinical laboratory value will be tabulated. The percentages will be calculated based on the denominator of the number of participants with available non-PCS baseline values and at least one post-baseline value and the numerator of the number of participants with non-PCS baseline value and at least one PCS post-baseline value. A supportive listing of participants with post-baseline PCS values will be provided.

In addition, a tabular display showing all AEs that occurred in participants who had PCS postbaseline clinical laboratory values will be provided.

Shift tables from baseline to the end of Intervention Period for clinical laboratory parameters listed above will be presented by study intervention group for the following categories: low, normal, and high, which are provided by lab vendor.

Potential Hy's Law Cases

Potential Hy's Law criteria within a 24-hour window is defined by a post baseline elevation of ALT or AST $\geq 3 \times \text{ULN}$, along with TBL $\geq 2 \times \text{ULN}$ and a non-elevated ALP $< 2 \times \text{ULN}$, all based on blood draws collected within a 24-hour period.

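### The SAP plans no systematic summary of urine glucose, protein, blood, ketones or reflex microscopy, and phosphate is the one measured electrolyte without a limit for potentially clinically significant (PCS) values

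*Protocol*

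**What the plan says.** **What is collected.** The Protocol Synopsis (Section 1.1) lists, among the assessments for the single objective, "clinical laboratory assessments (clinical chemistry, complete blood count [CBC], urinalysis". Table 10-1 in Protocol Section 10.2 sets the parameters. For urine these are specific gravity and pH, then "glucose, protein, blood, ketones microscopic examination (if blood or protein is abnormal". The chemistry panel includes "Potassium Sodium Bicarbonate Magnesium Phosphate Total Protein Total Bilirubin Calcium", and chloride appears elsewhere in the same panel. The schedules of activities place clinical laboratory tests at the end-of-treatment (EOT) visit for everyone, and also at screening for those who enroll more than 28 days after the lead-in study.

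**What the protocol promises.** Protocol Section 9.4.2 says that descriptive statistics at baseline, and changes from baseline, "will be presented by study intervention group for each clinical laboratory assessment". On PCS values it says only this: "The criteria for PCS laboratory values will be detailed in the SAP".

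**What the SAP plans.** SAP 9.3 gives a list of parameters for its laboratory summaries. Its urine entry is "Urinalysis: Specific gravity and pH". Its chemistry entry does contain phosphate: "bicarbonate, magnesium, phosphate, total protein, calcium, aspartate aminotransferase (AST". The shift tables refer back to the same list. A value is PCS "if they meet either the lower-limit or higher-limit PCS criteria listed in Table B-1", and the PCS listing and the display of AEs in participants with PCS values both follow from that flag.

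**The concern.** Urinalysis is one of three laboratory panels behind the safety objective. If the SAP is followed as written, the report's urinalysis tables rest on specific gravity and pH. New proteinuria, hematuria, glycosuria or ketonuria would not be counted by study intervention group. Whether such a result is visible would depend on each investigator's judgement of clinical significance, and a systematic table is meant not to depend on that judgement.

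The phosphate gap is smaller. The adverse events of special interest (AESIs) include significant electrolyte abnormalities related to diarrhea (SAP 9.2.6). Six measured electrolytes are screened with the same PCS multipliers; phosphate is measured and summarized but not screened. A reader of the PCS table would see no phosphate findings and could not tell from the table that none were possible.

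**Working it through.** No sample size, power or error rate is involved. The check compares three parameter lists: Protocol Table 10-1 (collected), SAP 9.3 (descriptive statistics and shifts) and SAP Table B-1 (PCS limits). Parameters printed twice in Table 10-1 are counted once, and reflex microscopy counts as one urine item.

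| Panel | Collected | In SAP 9.3 | With a PCS limit |
|---|---|---|---|
| Chemistry | 19 | 19 | 16 |
| Hematology | 13 | 13 | 10 |
| Urinalysis | 7 | 2 | 2 |
| Total | 39 | 34 | 28 |

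**Step 1: collected but absent from SAP 9.3.** 39 − 34 = 5. All five are urine items: glucose, protein, blood, ketones and reflex microscopy. Without the conditional microscopy, 4 of the 6 routine urine measures are missing (4/6 = 67%); with it, 5 of 7. Chemistry and hematology match the protocol fully, so the gap is confined to urine.

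**Step 2: trace each SAP 9.3 output for those five.**
- Descriptive statistics and change from baseline: listed parameters only, so none.
- Shift tables: the same list, so none.
- PCS table, PCS listing and linked AE display: these need a Table B-1 row, and its only urine rows are pH and specific gravity, so none.

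**Step 3: in SAP 9.3 but without a PCS limit.** 34 − 28 = 6: phosphate, direct bilirubin, indirect bilirubin, MCV, MCH and MCHC. Phosphate is the only electrolyte among them.

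**Step 4: the electrolytes.** Sodium, potassium, chloride, bicarbonate, calcium and magnesium each have a Table B-1 row with the same limits, < 0.9 × LLN and > 1.1 × ULN. Phosphate has none, so 6 of 7 are screened and 1 of 7 (14%) is not.

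**Step 5: what phosphate still gets.** It has descriptive statistics, change from baseline and a low/normal/high shift. The shift counts a value just below the laboratory limit and one far below it alike. If the descriptive set in SAP 7.0 is used, the minimum would show the most extreme value in a group, but not how many participants had a marked one.

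**The case against.** Four arguments on the other side deserve weight.

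**The protocol wording suits numeric results.** Section 9.4.2 speaks of values in SI units and changes from baseline. That fits specific gravity and pH and does not fit graded results or conditional microscopy. A reader might infer that SAP 9.3 plainly breaches the protocol. The documents do not support so firm a reading: the reference to each assessment keeps the urine point arguable, but a restriction to numeric parameters is a possible interpretation. For phosphate there is no breach at all, because the protocol leaves PCS criteria to the SAP and never promises a limit for every analyte.

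**Other outputs may exist.** SAP 1.0 places table and listing specifications in a separate document, which is not available here. A reader might infer that these urine results get no output whatsoever. That cannot be shown; what can be shown is that the SAP text names no summary of them.

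**Important abnormalities have another route.** Protocol Sections 8.2.4 and 10.3.1 have investigators review laboratory reports and record clinically significant abnormalities, urinalysis included, as AEs. SAP 9.2.3 tabulates treatment-emergent AEs and lists all AEs; SAP 9.2.6 tabulates and lists AESIs. This stands. A low phosphate judged significant and related to diarrhea would appear there. The route does not replace a systematic count, since it depends on individual judgement; if it were enough, no laboratory table would be needed.

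**The AESI link is limited.** A reader might infer that the plan hides the AESI signal. The documents never tie urine glucose, protein, blood or ketones to the AESI. Specific gravity, BUN, creatinine, hematocrit, the six other electrolytes, and postural blood pressure and pulse all keep PCS criteria. The AESI argument therefore bears only on phosphate, and there only in part.

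**Conclusion.** The point holds in two parts of unequal weight.

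- **Urinalysis.** Data collected for the primary safety objective have no systematic summary in the SAP text. The version history (SAP 12.0) records no decision to leave them out.
- **Phosphate.** Its missing Table B-1 row is an unexplained inconsistency within the SAP. Five non-electrolyte parameters also lack limits, so a missing row is not in itself unusual; what stands out is that the other six electrolytes share one rule.

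The size is modest. The percentages count analytes, not effects on a conclusion. There is no hypothesis or inferential test, and the only scheduled post-baseline laboratory sample in this study is at EOT. The gap concerns every participant with an EOT sample, except that microscopy applies only where blood or protein is abnormal. It is worth correcting because following the SAP exactly leaves collected safety data out of the named summaries.

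This rests on three assumptions: that the SAP 9.3 list is meant to be complete, that the four urine measures are reported in grades, and that the separate output specification does not already fill the gap. The grouping of seven electrolytes is ours; neither document labels such a set.

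**What to change.** 1. **SAP 9.3, urinalysis.** Add urine glucose, protein, blood and ketones as categorical parameters, with a shift from baseline to the end of the intervention period by study intervention group, separately for FC and IBS-C. Use the laboratory's reporting grades, for example negative, trace and positive. List the reflex microscopy results.
2. **SAP Table B-1, phosphate.** Add a row, by default with the multipliers already used for the other six electrolytes (< 0.9 × LLN, > 1.1 × ULN), or state why phosphate is excluded. The documents give no phosphate-specific basis for a threshold, so the default is a choice for consistency that the sponsor should confirm.
3. **Cross-reference.** If the separate output specification already contains these summaries or listings, say so in SAP 9.3.

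The SAP takes the lead-in baseline for participants who enroll within 28 days. The urine shift can include them only if the lead-in study recorded the same measures; the documents do not say, so the table should show the number with a missing baseline.

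The cost is SAP wording and a few extra descriptive tables and a listing, from data already collected. No samples or visits are added.
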